### **Administration of Human Allogeneic MSCs**

The study will enroll a minimum of 30 subjects and will consist of 2 cohorts. Enrolled subjects will be randomized at 1:1 into an experimental group (n=15) or a placebo group (n=15). Subjects in the experimental group will receive 1.5 million cells per kg, and subjects in the placebo group will receive 1 mL/kg LRS at days 0, 30 and 60.

After the subject is randomized into one of the two cohorts, the final formulation of MSC or placebo will be prepared. Within 8 hours of infusion, the appropriate number of cells will be thawed at the study site pharmacy and re-suspended in LRS at a concentration of  $1 \times 10^6$  cells/mL. Subjects in placebo group will receive LRS at a volume of 1.5 mL/kg. The study solution (MSCs or placebo) will be labeled to ensure investigator blinding. The solution will be labeled to indicate that it is an investigational agent and will contain subject's identifying information, date, and time of formulation.

An intravenous line will be placed into a peripheral vein, and 0.9% sodium chloride solution will be run to keep the vein open. The study product will be drawn using an 18-gauge needle into a 60 mL syringe with an eccentric tip. The needle will be removed, and infusion tubing will be attached to the syringe. The syringe with infusion tubing will be placed in a metered dose syringe pump positioned horizontally with the syringe rotated such that the syringe tip is at the lowest position. The product will be infused intravenously into the subject's arm at a constant rate of approximately 2 mL/min. The applicable volume for the target dose will be delivered within  $\pm 2$  mL. Depending on subject's weight, up to three 60 ml syringes of product may be infused. After the entire product volume is delivered, 25 mL of LRS (without cells) will be infused at 2 ml/min to deliver cells from the infusion line for more accurate dosing. Subjects in the placebo group will receive intravenous LRS. Their syringes will be labeled as above to preserve blinding and followed by 25 ml of LRS infusion as above.

If the subject has an adverse reaction during the infusion, the infusion may be interrupted or slowed according to the severity of the reaction.

The following symptoms, if noted, during infusion may lead to slowing or cessation of the infusion session:

- Temperature  $\geq 39^{\circ}\text{C}$ .
- Unexplainable shaking chills.
- Angioedema.
- Respiratory distress.
- Wheezing/bronchospasms.

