4. The PI/designee will notify Stemedica point person within 24 hours of receipt of report from lab.
5. The PI will determine whether the FDA and IRB need to be notified immediately (e.g. if there is a serious adverse event) or if this will be included in the progress report. Standard reporting of adverse events will be followed as specified in the protocol.
6. The notification and workup for positive culture form will be completed (form attached).
7. All products with positive cultures will be marked with a biohazard label.

8. The retention sample will be sent to the microbiology lab for testing.
9. All the materials will be maintained until further instruction is received from Stemedica.
10. Stemedica staff to investigate failure and determine if further formulation activities or testing is required to support investigation of the issue.

The study will enroll a minimum of 30 subjects and will consist of 2 cohorts. Enrolled subjects will be randomized at 1:1 into an experimental group (n=15) or a placebo group (n=15). Subjects in the experimental group will receive 1.5 million cells per kg and subjects in the placebo group will receive 1.5 mL/kg Lactated Ringer's Solution.

Once the subject is randomized into one of the two cohorts, the cells or placebo will be prepared. Within 8 hours of infusion, the appropriate number of cells will be thawed at the study site pharmacy and re-suspended in Lactated Ringer's Solution (LRS) at a concentration of  $1 \times 10^6$  cells/mL. Subjects in placebo group will receive LRS at a volume of 1.5 mL/kg. The study solution (cells or placebo) will be labeled to indicate that it is an investigational agent and will contain a subject's information, date, and time of formulation.

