## **6.2 IV Administration of MSCs or Placebo**

An intravenous line will be placed into an appropriate peripheral vein with 0.9% sodium chloride solution running to keep the vein open. The study solution described above will be taken up in an 18 gauge needle into a 60 mL syringe with an eccentric (offset) tip. The needle will be removed and infusion tubing will be attached to the syringe. The syringe with infusion tubing will be placed in a metered dose syringe pump positioned horizontally with the syringe rotated such that the syringe tip is at the lowest position. The product will be infused intravenously into the subject's arm at a constant rate of approximately 2 mL/min. The applicable volume for the target dose will be delivered within 2 mL. Depending on subject's weight, up to three 60 mL syringes of product may be infused. After the entire product volume is delivered, 25 mL of LRS (without cells) will be infused at 2 mL/min to deliver cells from the infusion line for more accurate dosing. Subjects in the placebo group will receive intravenous LRS. Their syringes will be labeled as above to preserve blinding and followed by 25 mL of LRS infusion as above.

If the subject has an adverse reaction during the infusion, the infusion may be interrupted or slowed according to the severity of the reaction. All appropriate treatment will be given to reduce any discomfort and ensure the subject's safety. The infusion may be restarted, if interrupted, if the subject is not considered to be at risk by the Investigator and the subject consents.

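### If the three-syringe allowance is a maximum, the per-kg cell dose and the 2 mL tolerance cannot both be met above about 121 kg, and no eligibility criterion limits weight

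*Combined protocol and SAP*

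**What the plan says.** Dose: Section 6.1 states "Subjects in the experimental group will receive 1.5 million cells per kg", and Section 4.1, Section 5.1 and the text under Administration of Human Allogeneic MSCs give the same figure.

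Concentration: the Administration text says that "the appropriate number of cells will be thawed at the study site pharmacy and re-suspended in LRS at a concentration of" 1 x 10^6 cells/mL. Section 6.1 repeats that concentration.

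Placebo volume: the Administration text says "Subjects in placebo group will receive LRS at a volume of 1.5 mL/kg". Sections 4.1, 5.1, 5.2 and 6.1 agree.

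Syringes: the Administration text says that, according to weight, "up to three 60 ml syringes of product may be infused". Section 6.2 repeats it: "Depending on subject's weight, up to three 60 mL syringes of product may be infused".

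Precision: Section 6.2 says "The applicable volume for the target dose will be delivered within 2 mL". The Administration text gives the same tolerance as plus or minus 2 mL. A 25 mL flush follows; it contains no cells, so it adds nothing to the dose.

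Weight: the eight inclusion and 25 exclusion criteria in Section 5.1 contain no weight or BMI limit. No section states a maximum cell dose, provides for a fourth syringe or another concentration, or says what to do when the calculated volume exceeds 180 mL.

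**The concern.** The dose rises with weight without limit, while the syringe sentence gives an upper number of syringes. On its ordinary reading as a maximum, there is a weight above which a site cannot follow the per-kg dose, the 2 mL tolerance and the syringe count together. Nothing in eligibility keeps such a subject out, and nothing in the administration text says which statement gives way.

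Two things are at stake. First, a heavy cell-arm subject could receive fewer cells per kg than stated, by more than the protocol's own tolerance. This could go unnoticed, because the text asks for infusion reactions, slowing, stopping and resumption to be recorded on the case report form but does not list delivered volume. Second, with up to two sites (Section 5.2), staff could resolve the conflict differently. If they did so differently by arm, the volume infused or the number of syringes could differ between arms in a double-blind trial.

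**Working it through.** **Inputs, all from the protocol**
- Dose: 1.5 million cells/kg (Administration text; Sections 4.1, 5.1, 6.1)
- Concentration: 1 x 10^6 cells/mL (Administration text; Section 6.1)
- Syringes: up to three of 60 mL (Administration text; Section 6.2)
- Tolerance: 2 mL (same two places)
- Upper weight limit: none (Section 5.1)

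The calculation takes 60 mL as the usable volume of each syringe and three as a maximum.

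**Step 1: reproduce the plan's own volume.** Volume per kg = dose / concentration = 1,500,000 / 1,000,000 = 1.5 mL/kg. This equals the stated placebo volume of 1.5 mL/kg, so dose, concentration and placebo volume agree.

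**Step 2: volume available.** 3 x 60 = 180 mL.

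**Step 3: weight at which the full volume just fits.** 180 / 1.5 = 120 kg.

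**Step 4: allow for the tolerance.** Delivery may fall 2 mL below target, so 180 mL still complies when the target is 182 mL: 182 / 1.5 = 121.3 kg. At 121 kg, for example, the target is 181.5 mL and the shortfall of 1.5 mL is within tolerance.

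**Step 5: shortfall beyond that point.** Needed volume = 1.5 x weight; shortfall = needed volume - 180; share of dose = 180 / needed volume. The weights are illustrative.

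| Weight (kg) | Needed (mL) | Shortfall (mL) | Share of stated dose | Cells/kg (million) |
|---|---|---|---|---|
| 120 | 180 | 0 | 100% | 1.50 |
| 122 | 183 | 3 | 98% | 1.48 |
| 130 | 195 | 15 | 92% | 1.38 |
| 140 | 210 | 30 | 86% | 1.29 |
| 150 | 225 | 45 | 80% | 1.20 |

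**Step 6: who could be affected.** Only the 15 experimental subjects receive cells, so each affected subject there is 1/15 = 6.7% of the arm. A placebo subject of the same weight would have a discrepancy in fluid volume only. The documents give no weights, so no expected count can be derived.

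**A related inconsistency.** The Administration text also says "subjects in the placebo group will receive 1 mL/kg LRS at days 0, 30 and 60", against 1.5 mL/kg elsewhere in the same text. At 1 mL/kg, 180 mL would suffice for placebo up to 180 / 1 = 180 kg. This is a separate contradiction and leaves the cell-dose result unchanged, but on that figure the syringe limit would be reached at different weights in the two arms.

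**The case against.** The strongest reply is that the syringe sentence is permissive. It says what may be infused, whereas the neighbouring sentences say that the target volume will be delivered and that the flush follows once all of the product is in. On that reading the weight-based volume governs, the syringe count only describes expected logistics, and a heavier subject would simply need a further syringe. This stands as a possible reading. A reader might infer that the stated dose is impossible to deliver above 120 kg; the documents do not support that. The conflict depends on reading the count as a maximum, and even then it begins at about 121 kg. But the sentence ties the count to weight and gives an upper number, so a maximum is the more natural reading, and sites could take it either way.

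A second reply is that the manufacturer's Pharmacy Manual may cover the case. Section 6.1 cites that manual for storage and handling and does not refer to it for this limit. It is not among the documents, so a rule there can be neither confirmed nor excluded; if one exists, the protocol text should agree with it. Exclusion criterion 15 leaves room for investigator or sponsor judgment but does not mention weight.

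A third reply is that the effect on the analysis is negligible. This largely stands. A reader might infer that the safety conclusion would rest on a wrong exposure. Sections 9 and 9.2 plan descriptive summaries by treatment actually received and Fisher's exact tests on adverse events, and no planned analysis uses cells per kg. A partial shortfall would not move a subject to the other arm or change how that subject is counted.

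Finally, weight is already measured before each infusion (Section 7.2.2), and Section 10.8 requires product accountability records. These help, but neither explicitly captures the volume that reached the subject.

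**Conclusion.** The point holds as a minor inconsistency in the administration text. If up to three syringes means at most three, and each gives 60 mL, the per-kg dose, the 2 mL tolerance and the syringe count cannot all be met above about 121 kg (120 kg if the tolerance is not used), and eligibility does not exclude such subjects. The shortfall grows with weight and soon exceeds the tolerance many times over: 30 mL against 2 mL at 140 kg.

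How many subjects this touches is unknown and may be none. A count out of all 30 would need a weight distribution that the documents do not give, and would include placebo subjects, who cannot be under-dosed in cells. The consequence is limited to the dose a heavy cell-arm subject receives and to consistency between sites and arms.

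**What to change.** The sponsor should reconcile the syringe limit, the per-kg dose and the volume tolerance in the Administration text and in Section 6.2, or state there that the syringe count is only descriptive. Which passage changes is for the sponsor to decide; no dose, weight limit or clinical rule is proposed here. Whatever is chosen should apply identically in both arms, so that infusion volume and syringe count do not reveal the assignment. The two placebo volumes in the Administration text should be reconciled in the same edit.

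The delivered volume should be recorded for each infusion. With the pre-infusion weight already collected and the stated concentration, cells per kg in the cell arm can then be computed without a further field.

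The cost is about one sentence in each of the two places and one case report form field.

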## **CONCOMITANT THERAPY AND CLINICAL PRACTICE**

Subjects will continue all of their regular medications unless contraindicated. Subjects may be administered beta-blockers, ACE inhibitors, angiotensin receptor blockers or angiotensin receptor neprilysin inhibitor, mineralocorticoid receptor antagonists, isosorbide, hydralazine, statins, or other medications, as tolerated. Goal mean arterial BP will be  $<85$  mmHg. LVAD speed will be maintained, unless there is a compelling clinical indication to change it. Changes in pump speed should be approved by the PI, unless emergency.

## 4.2 Endpoints

### PRIMARY ENDPOINT

#### **Safety of MSCs assessed at the following time-intervals:**

Baseline and days 30, 60, 90, 180, and 360 post-initial infusion

1. Procedural complications
2. Vital signs
  - a. Temperature
  - b. Mean arterial blood pressure
  - c. Heart rate
  - d. Respiratory rate
  - e. Weight
  - f. LVAD parameters: Pump speed, flow, pulsatility and power
3. Uncontrolled systemic infection.
4. Hemodynamically unstable clinical arrhythmias that require appropriate defibrillator shock, anti-tachycardia pacing or initiation or escalation of antiarrhythmic medications.
5. Laboratory tests
  - a. Complete blood count (CBC)/ differential.
  - b. Comprehensive Metabolic Panel: Sodium, potassium, chloride, bicarbonate, blood urea nitrogen (BUN), creatinine, glucose, calcium, magnesium and liver function tests (ALT, AST, alkaline phosphatase, bilirubin and albumin)
  - c. Troponin-I.
  - d. Allosensitization (change in antibodies against HLA (panel reactive antibody test) from baseline for strong HLA antibody specificities (MFI>2000))
6. Electrocardiogram.
7. All-cause mortality. This will be reviewed by the DSMB. The LVAD population is a high risk group with very

high mortality, which will be taken into account when reviewing safety. Survival rate among HF patients with LVAD is 95% at 1 month, 81% at 1 year, 70% at 2 years, 59% at 3 years and 49% at 4 years. For patients enrolled within our study window, we would expect a 20% mortality rate in our patient population.

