One of the investigators of the present trial was co-PI of a trial testing the effects of IV administration of MSCs in patients with NICM. The MSCs used in the present trial will derive from the same donor and will have undergone the same growth and expansion methods (undertaken by Stemedica) as were used in the prior trial. The study was a Phase 2a randomized, single blind, placebo controlled, crossover, multicenter trial consisting of 23 patients with NICM. Crossover occurred at 90 days after study initiation and study termination occurred at 180 days.

Compared to placebo, IV MSCs:

- Significantly increased 6-minute walk distance.
- Significantly improved Kansas City Cardiomyopathy scores.
- However, there were no significant changes from baseline in LV function between the two groups.

Of great interest, IV administration of MSCs decreased circulating NK cells, and *the magnitude of MSC-induced decrease in NK cells correlated with the magnitude of improvement in LV function* (Fig 4.1).

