***Patients with Chronic Obstruction Pulmonary Disease (an immunocompetent cohort of patients).***

Sixty-two patients with chronic obstruction pulmonary disease (COPD) were randomized to double-blinded IV infusions of either allogeneic MSCs or vehicle control. Patients received four monthly infusions ( $100 \times 10^6$  cells/infusion) and were subsequently followed for 2 years. The authors report that "There were no infusional toxicities and no deaths or serious adverse events (SAEs) deemed related to MSC administration. There were no significant differences in the overall number of adverse events, frequency of COPD exacerbations, or worsening of disease in patients treated with MSCs."

In our study, during MSC infusion, we will carefully observe our patients to determine whether clinically important safety-related immune response issues arise acutely.

We will also test for long-term development of immune cell reactivity, development of anti-HLA antibodies, and whether any positive test responses are associated with adverse clinical outcomes.

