## 4 STUDY DESIGN

### 4.1 Description of the Study

This is a Phase IIa, double blind, placebo-controlled, multi-center, randomized study in subjects with advanced HF who are supported by LVADs.

The study will enroll 30 subjects and will consist of 2 cohorts. Enrolled subjects will be stratified by LVAD device type (HeartWare HVAD, HeartMate II or HeartMate III) and randomized at 1:1 into an experimental group (n=15) or a placebo group (n=15), respectively. Subjects in the experimental group will receive 1.5 million cells per kg, and subjects in the placebo group will receive 1.5 mL/kg Lactated Ringer's Solution at baseline, 1 month and 2 months.

All study participants will receive the MSCs or placebo within  $\pm 7$  days of the specified timing.

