## **SUBJECT PARTICIPATION**

Eligible participants must have advanced HF of ischemic etiology, defined as 1) a prior history of myocardial infarction and/or 2) angiographically (invasive or cardiac CT angiography) documented significant CAD (defined as a prior history of coronary revascularization (CABG or PCI) and/or obstructive CAD ( $\geq 75\%$  stenosis of the left main or proximal LAD or  $\geq 75\%$  stenosis of two or more major epicardial coronary arteries)) or non-ischemic cardiomyopathy etiology.

Enrollment window will open after discharge from index implant hospitalization and once the patient has been deemed stable with their LVAD implantation.

The screening evaluation will include obtaining written informed consent, collection of a complete medical history, including current and past medications, physical examination and laboratory tests. LVAD implantation is required for inclusion in the study.

A comprehensive 2D and 3D and 3D and Doppler transthoracic echocardiography with speckle tracking and gated blood pool SPECT ventriculography for assessment of right and left ventricular systolic function and volumes will be performed at baseline and at the specific time points during follow-up.

Eligible subjects will receive repeated infusions of either MSCs or placebo based on randomization at time 0 and at day 30 ( $\pm 7$  days) and day 60 ( $\pm 7$  days).

Follow-up visits will occur at days 7 ( $\pm 2$  days), 30 ( $\pm 7$  days), 37 ( $\pm 2$  days), 60 ( $\pm 7$  days), 67 ( $\pm 2$  days), 90 ( $\pm 7$  days), 180 ( $\pm 7$  days), and 360 ( $\pm 7$  days). Information on AEs, concomitant medications, vital signs, clinical laboratory tests and physical examination will be collected according to the schedule of assessments (Appendix A). All guideline-based medical care will continue as prescribed by the subject's personal physician(s). Use of other investigational agents or treatments is not allowed during this study.

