### **6.4 Concomitant Medications and Rehabilitation**

Concomitant medications (any prescription and/or over-the-counter preparations) and therapies (nondrug or procedures) used by a subject while participating in this clinical trial will be optimized per the AHA Guidelines and recorded at screening and until the end of the study or the end of a subject's participation in the study.

Subjects may be administered beta-blockers, ACE inhibitors, angiotensin receptor blockers or angiotensin receptor neprilysin inhibitor, mineralocorticoid receptor antagonists, isosorbide, hydralazine, statins, or other medications, as tolerated. All other prescription and over-the-counter preparations approved by the patients' physician will be permitted.

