## 2. Cellular response

At all-time points leukocytes will be isolated from blood samples and will be frozen for further analysis.

Leukocytes will be analyzed for:

Immune phenotyping by flow cytometry, to determine the effect of treatment with MSCs on the cellular immune response. (Expected effect - changing the balance from pro to anti-inflammatory phenotype).

Functional assays.

Proliferation assay – evaluating the suppressive effect of MSCs on T cells.

In-vitro cytokine secretion – testing the effect of MSCs treatment on leukocytes potential to secret cytokines following general stimulation.

Cytotoxicity assay – co-culture of leukocytes with MSCs will test the cytotoxic effect of leukocytes toward MSCs on the axis of time and repeated treatments. This assay will help evaluating the effectiveness of repeated treatments with MSCs.

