### **9.3 Determination of Sample Size**

This Study is exploratory and its sample size is not determined by statistical power considerations, but is considered appropriate for an early phase safety trial.

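### Primary item 5d counts strong HLA antibodies of any specificity although all the cells come from one donor, so a new antibody cannot be attributed to the cells; HLA is also not drawn at early termination

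*Combined protocol and SAP*

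**What the plan says.** Section 4.2 lists allosensitisation as item 5d of the primary safety endpoint: "Allosensitization (change in antibodies against HLA (panel reactive antibody test) from baseline for strong HLA antibody specificities (MFI>2000". It refers to specificities and sets an MFI cut-off. It does not ask whether a specificity matches an antigen of the cell donor, and it does not say whether a change means a new specificity, a rise in MFI or a rise in panel percentage.

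Background section 4 gives the cell source: "The MSCs used in the present trial will derive from the same donor" as in the earlier NICM trial. One donor HLA type therefore applies to every subject in the MSC arm.

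Background section 8 says the trial will test for "development of anti-HLA antibodies, and whether any positive test responses are associated with adverse clinical outcomes".

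Sections 7.1, 7.2.2 and 7.3 and Appendix A list the sample only as HLA. Appendix A schedules it at each infusion visit and at days 90, 180 and 360. Section 7.4 (Early Termination Visit) does not list it, and the Early Term cell of the Appendix A HLA row is blank.

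Section 9 makes no substitution for missing data. Section 9.2 puts laboratory data into shift tables and change-from-baseline summaries and gives no attribution rule for HLA antibodies.

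**The concern.** Background sections 8 and 9 treat the immune response to repeated allogeneic doses as both a safety question and an efficacy question. Item 5d is the antibody measure that bears on it. An any-specificity result answers whether a subject formed strong HLA antibodies. It does not answer whether those antibodies are directed at the infused cells.

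Two things are at stake. First, any new antibody unrelated to the cells appears in both arms and dilutes a cell-induced excess, which is hard to see at 15 per arm in any case. Second, the outcome analysis promised in Background section 8 works on individual positives. Randomisation does not label an individual positive as cell-directed or not, so that analysis would combine two kinds of antibody that may carry different risks.

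Separately, a subject who leaves the study has no closing value for this primary item, although blood is drawn at the early termination visit for other tests.

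**Working it through.** The plan states no rate, alpha or power for this item, so there is no figure to reproduce. The calculation is an illustration with assumed rates.

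**Inputs**
- From section 4.1: subjects are "randomized at 1:1 into an experimental group (n=15) or a placebo group (n=15"), so n = 15 per arm.
- Assumed: d = 20% of MSC subjects form cell-induced, donor-directed antibodies.
- Assumed: b = 20% of subjects in each arm form new background antibodies after baseline (range 10–30%), independently of d.
- Assumed: m = 2%, 4% or 10% of subjects have background antibodies that match the donor. At b = 20% this is 10%, 20% or 50% of the background-positive subjects.
- Simplification: each subject is positive or negative.

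**Formulas**
- Any-HLA item: MSC rate = 1 − (1 − d)(1 − b); placebo rate = b.
- Donor-matched item: the same with m in place of b.
- Dilution: the arm difference is d(1 − b).
- No excess: P(MSC count ≤ placebo count), from two independent binomials with n = 15.
- Share of MSC-arm positives with no cell-induced antibody: (MSC rate − d) / MSC rate.

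**Any-HLA item at b = 20%**
- MSC rate = 1 − 0.80 × 0.80 = 0.36; placebo rate = 0.20.
- Expected counts: 15 × 0.36 = 5.4 against 15 × 0.20 = 3.0.
- Difference: 0.36 − 0.20 = 0.16, down from 0.20.
- Unrelated share of MSC positives: (0.36 − 0.20) / 0.36 = 44%.

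**Results for d = 20%**

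| Item | Background counted | Expected MSC v placebo | P(no MSC excess) | Unrelated share of MSC positives |
|---|---|---|---|---|
| Any-HLA | 10% | 4.2 v 1.5 | 0.14 | 29% |
| Any-HLA | 20% | 5.4 v 3.0 | 0.21 | 44% |
| Any-HLA | 30% | 6.6 v 4.5 | 0.27 | 55% |
| Donor-matched | 2% | 3.2 v 0.3 | 0.06 | 7% |
| Donor-matched | 4% | 3.5 v 0.6 | 0.09 | 14% |
| Donor-matched | 10% | 4.2 v 1.5 | 0.14 | 29% |

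The percentages in the second column are percentages of subjects, not of antibodies. The gain depends on how much of the background happens to fall on donor antigens.

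**Outcome analysis.** If it pools the arms, the any-HLA item at b = 20% gives 5.4 + 3.0 = 8.4 expected positives. Of these, 15 × 0.20 = 3.0 carry a cell-induced antibody, which is 36%.

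**Limits of the gain.** Section 9.2 names Fisher's exact test for adverse events only. If it were applied here at a two-sided 0.05 level (assumed) with d = 20% and b = 20%, power would be 8% on the any-HLA item and 12–16% on the donor-matched item when 0–50% of the background matches. With d = 40% it would be 28% against 45–78%, and the any-HLA no-excess probability would fall to 0.04. The split helps description and attribution. It does not make a small effect testable.

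**Early termination.** Section 7.4 and the Appendix A HLA row agree that no sample is taken. With the no-substitution rule in section 9, the subject's last value is from the last scheduled visit attended.

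**The case against.** The case against has several sound parts.

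- **Baseline and control.** Item 5d is a change from baseline, and "Enrollment window will open after discharge from index implant hospitalization", so antibodies already present from the implant admission are in the baseline. The concurrent 1:1 placebo arm estimates whatever background remains. A reader might infer that background antibodies bias the arm comparison. They do not in expectation; they only dilute it.
- **Cause of the background.** A reader might infer that transfusion or the LVAD raises these antibodies. The documents name neither as a cause and give no background rate. Section 6.4 does not mention blood products; it only requires recording of "therapies (nondrug or procedures) used by a subject while participating in this clinical trial". The point needs only that some new antibodies may be unrelated to the cells, and their frequency here is an assumption.
- **A cell-specific assay exists.** In section 7.1, "co-culture of leukocytes with MSCs will test the cytotoxic effect of leukocytes toward MSCs". This bears on the same question, but it measures leukocytes rather than antibodies and is not part of item 5d.
- **The study is descriptive.** Section 9.3 says "its sample size is not determined by statistical power considerations", and 5d is one of many safety items. No formal conclusion depends on this contrast. That limits the harm, but a descriptive study still benefits from a measure that can be interpreted.
- **The split could be made later** from stored specificities, in the SAP that section 9 promises before analysis. This is true if the laboratory keeps results by specificity and the donor's type is known, and the documents state neither. The missing early termination sample cannot be recovered.
- **Subjects who react to an infusion.** A reader might infer that a subject whose infusion is stopped for a reaction gives no later HLA value. The section on administering the cells says that such a subject continues with scheduled follow-up, where HLA is drawn. The gap concerns subjects who leave the study, and their earlier values remain.

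**Conclusion.** The point holds as one of attribution and dilution, not bias. Item 5d takes HLA antibodies of any specificity although the product has a single donor, and the plan has no rule for linking a new antibody to the cells. The outcome analysis in Background section 8 is affected most directly.

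Under the assumed rates, the chance that a real 20% cell-induced effect shows no excess falls from 0.21 to between 0.06 and 0.14 with a donor-matched measure, and the unrelated share of MSC-arm positives falls from 44% to between 7% and 29%. These sizes rest on assumed cell-induced, background and matching rates and on independence between the two sources. The textual finding does not. That matching is possible is an inference from the single donor and the use of specificities; the documents do not say that the donor's HLA type is available.

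The absence of HLA from the early termination visit needs no assumption. It is a small, separate gap in a primary item.

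**What to change.** 1. Keep the any-HLA summary in item 5d and state what counts as a change. Add, by arm and visit, new or rising specificities with MFI above 2000 that match the MSC donor's HLA type, as the cell-attributable measure. Use the split in the analysis of antibodies against outcomes.
2. Have the laboratory or an unblinded statistician hold the split until database lock, because a donor-matched result would point to the arm.
3. Add the HLA sample to section 7.4 and to the Early Term column of the Appendix A HLA row.

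The cost is wording in the protocol and SAP, one HLA typing of the cell bank if none is on file, one tube at a visit that already draws blood, and control of an unblinding result. Sample size and the visit schedule do not change.
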